#### 8.4.2 Collection, Recording and Reporting of Serious Adverse Events

##### Serious Adverse Event Reporting by the Investigator

All serious adverse events must be reported **immediately** to Ferring Global Pharmacovigilance as soon as it becomes known to the investigator and not later than within 24 hours of their knowledge of the occurrence of a serious adverse event.

The investigator is responsible for submitting the completed Serious Adverse Event (SAE) Report Form with the fullest possible details **within 3 calendar days** of his/her knowledge of the serious adverse event.

##### Serious Adverse Event (SAE) Report Form

The SAE Report Form is included in the e-CRF system, and must be completed and submitted according to the instructions provided on the form. In case the e-CRF cannot be accessed and hence the SAE Report Form cannot be filled in within the e-CRF system, a paper SAE Report Form should be used and sent to Ferring Global Pharmacovigilance using the contact details below.

Global Pharmacovigilance, Ferring Pharmaceuticals A/S

E-mail: [[contact]](mailto:[contact])

Fax: [REDACTED]

##### Information to be Entered / Updated in the e-CRF

Completion of the Demographics, Adverse Event form, Medical History form and Concomitant Medication form are mandatory for initial reports and for follow-up reports if any relevant changes have been made since the initial report. Data entries must have been made in the e-CRF for Ferring Global Pharmacovigilance to access the information.

---

h Major abnormalities: a life threatening structural anomaly or one likely to cause significant impairment of health or functional capacity and which needs medical or surgical treatment.

Minor anomalies: relatively frequent structural anomaly not likely to cause any medical or cosmetic problems.

Additional information relevant to the serious adverse event such as hospital records, results from investigations, e.g. laboratory parameters (that are not already uploaded in the e-CRF), invasive procedures, scans and x-rays, and autopsy results can be faxed or scanned and e-mailed to Ferring Global Pharmacovigilance using the contact details in the section above. In any case this information must be supplied by the investigator upon request from Ferring. On any copies provided, such details such as subject's name, address, and hospital ID number should be concealed and instead subject number should be provided.

The investigator will supply Ferring and the ethics committee with any additional requested information such as results of post-mortem examinations and hospital records.

### **Expedited Reporting by Ferring**

Ferring will report all adverse events that are **serious, unexpected and with a reasonable possible causality to the IMP** as judged by either the investigator or Ferring to the relevant parties within the stipulated timelines.

The expectedness is assessed by Ferring according to the current edition of the Investigator's Brochure for FE 999049 and the Product Information for GONAL-F.

Serious adverse events will be considered reportable regardless of whether or not the IMP was used in accordance with the provisions in the protocol, Investigator's Brochure and labelling.

## **8.5 Follow-up of Adverse Events and Serious Adverse Events**

### **8.5.1 Follow-up of Adverse Events with Onset during the Trial**

During the trial, the investigator must follow-up on each adverse event until it is resolved or until the medical condition of the subject is stable.

After the subject's last visit, the investigator must follow-up on any adverse event classified as serious or considered to have a reasonable possible causality to the IMP until it is resolved or until the medical condition of the subject is stable. All such relevant follow-up information must be reported to Ferring. If the event is a chronic condition, the investigator and Ferring may agree that further follow-up is not required.

### **8.5.2 Collection of Serious Adverse Events with Onset after End-of-trial**

If an investigator becomes aware of a serious adverse event after the end of the trial, and he/she assesses the serious adverse event to have a reasonable possible causality to the IMP (FE 999049 or GONAL-F) or a NIMP where Ferring is Marketing Authorisation Holder (i.e. GONAPEPTYL) the case will have to be reported to Ferring, regardless how long after the end of the trial this takes place.

### **8.5.3 Follow-up of Serious Adverse Events with Onset during the Post-Trial**

For post-trial serious adverse events in neonates, where the neonate has not recovered at the 4-weeks follow-up assessment, the investigator must follow up until SAE has resolved. If the SAE is a chronic condition or the medical condition of the neonate is stable, the investigator and Ferring may agree that further follow-up is not required.

## 9 STATISTICAL METHODS

The Ferring Global Biometrics Department will be responsible for the statistical analyses of the primary and secondary endpoints. This section details the planned statistical analyses for the primary endpoint and outlines the planned statistical analyses for the secondary endpoints. All analyses and further descriptions of the statistical methodology for the primary and secondary endpoints will be included in the Statistical Analysis Plan (SAP) available before the first subject is randomised. A separate SAP will be prepared to cover the post-trial information.

The Ferring Health Economics & Outcome Research department will perform a health economic analysis of FE 999049 in comparison with GONAL-F utilising relevant data recorded in this trial. The details of this analysis will be described in a separate health economic analysis plan.

### 9.1 Determination of Sample Size

The primary objective of this trial is to demonstrate non-inferiority of FE 999049 compared with GONAL-F with respect to ongoing pregnancy rate in women undergoing controlled ovarian stimulation. The non-inferiority limit for the difference between treatments (FE 999049 versus GONAL-F) is -10.0% (absolute) for the primary endpoint.

The trial is designed to have 90% power of achieving the primary objective for the overall trial population and 80% power in the mainland Chinese population. The number of subjects needed to achieve 90% power depends on the assumptions regarding the ongoing pregnancy rate. The ongoing pregnancy rate is defined as the number of subjects with at least one intrauterine viable fetus 10-11 weeks after transfer divided by the number of randomised and exposed subjects.

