### Considerations for Choice of Non-inferiority Margin

Assuming that the ongoing pregnancy rate is 32.2% in both treatment groups, then the total number of subjects needed to achieve 90% power is governed by the choice of non-inferiority margin. In order to establish non-inferiority, the two-sided 95% confidence interval must lie entirely above the chosen non-inferiority margin. Therefore, the power of the test is directly related to the width of the two-sided 95% confidence interval. The width of this confidence interval is inversely related to the square root of the sample size, i.e. a quadrupling of the sample size will lead to a halving of the width of the confidence interval. In fact, increasing the sample size with 500 subjects from 100 to 600 reduces the width of the confidence band with 59%, while the impact of a similar increase in number of subjects from 1,000 to 1,500 only reduces the width of the confidence band with 18%.

The sample sizes for three different non-inferiority margins are shown in Table 9-1. As shown, changing the non-inferiority margin from -12.0% to -10.0% requires 280 additional subjects, while tightening the margin with an additional 2.0% requires 516 additional subjects. To further illustrate the difference between these three non-inferiority margins, the width of the two-sided 95% confidence intervals and the precision quantified as  $\pm 1$  standard error are also included in Table 9-1. As can be seen, increasing the sample size from 918 to 1,434 subjects reduces the standard error with 0.6 percentage points (from 3.1% to 2.5%).

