### Considerations for Sample Size

Table 9-2 summarises the required sample size to obtain 80% and 90% power for various rates (assumed equal in the two treatment groups) and assuming a non-inferiority margin of -10.0% (absolute).

Since this is a non-inferiority trial, the full analysis set (FAS) and the per-protocol (PP) analyses are equally important, i.e. non-inferiority should be established for both analysis sets in order to have a robust conclusion. Therefore, the expected proportion of subjects with major protocol deviations should be taken into account when setting the total sample size for the trial. The proportion of subjects with major protocol deviations is assumed to be at most 8%.

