**Table 9-2 Sample Size by Ongoing Pregnancy Rate for the PP Analysis Set**

Ongoing pregnancy rate (Assumed equal in the two treatment groups)	Assuming 80% power and -10.0% (absolute) non-inferiority margin		Assuming 90% power and -10.0% (absolute) non-inferiority margin	
	Number of subjects		Number of subjects	
	Per group	Total	Per group	Total
	PP*	PP*	PP*	PP*
25%	295	590	395	790
30%	330	660	442	884
32.2%	343	686	459	918
35%	358	716	479	958
40%	377	754	505	1010
45%	389	778	521	1042
50%	393	786	526	1052

\* Assuming 8% major protocol deviations

Based on an assumed ongoing pregnancy rate of 32.2 % observed in the PP population of the ESTHER 1 trial, N=918 subjects are required in the PP population to obtain a power of 90%. Anticipating at most 8% major protocol deviations this results in N=1000 subjects to be randomised. The power is reasonably robust against deviations from the ongoing pregnancy rate assumption of 32.2%: a 35% ongoing pregnancy rate would still result in a 88.9% power, while lower rates will only increase the power (e.g. 30% yields 91.1% power). Recruiting at least 740 subjects in mainland China is expected to secure that consistency can be established between the results from the overall trial population and the mainland Chinese trial population. In addition, to obtain approval in other Asian countries and regions at least 260 subjects are needed. Thus a total sample size of 1,000 subjects will be recruited for this trial.

A sample size re-assessment is planned and will be done without breaking the blind and without inflating the type 1 error of the trial, in line with the current regulatory guidelines (see section 9.10). The expected maximum number of subjects to be randomised would then be approximately 1,144 (572 per treatment group), corresponding to an observed rate of 50%.

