### 9.7.2 Primary Endpoint

This trial has one primary endpoint: Ongoing pregnancy rate. The primary objective of this trial is to demonstrate non-inferiority of FE 999049 compared with GONAL-F with respect to the primary endpoint in women undergoing controlled ovarian stimulation. The non-inferiority limit for the difference between treatments (FE 999049 versus GONAL-F) is -10.0% (absolute).

The non-inferiority hypothesis to be tested for the primary endpoint is

$$H_0: \pi_{FE} - \pi_{GF} \leq -10.0\% \text{ against the alternative } H_A: \pi_{FE} - \pi_{GF} > -10.0\%,$$

where  $\pi_{FE}$  and  $\pi_{GF}$  denote the ongoing pregnancy rate after treatment with FE 999049 and GONAL-F, respectively. Non-inferiority will be evaluated based on the overall trial population.

The primary analyses will be adjusted for the stratification factor (age group) by using the Mantel-Haenszel method to combine results across age groups. In brief, this corresponds to deriving a weighted average across age groups where the weight depends on the number of observations in each treatment group in each age stratum.

For the primary endpoint the null hypothesis ( $H_0$ ) will be tested against the alternative ( $H_A$ ) by constructing a two-sided 95% confidence interval for the difference in ongoing pregnancy rates. If the lower-limit of the two-sided 95% confidence interval is greater than the non-inferiority limit (-10.0%) for both the FAS and the PP analysis set, the null hypothesis will be rejected. In that case it will be claimed that FE 999049 is non-inferior to GONAL-F with respect to ongoing pregnancy rate in women undergoing controlled ovarian stimulation.

If the lower-limit of the two-sided 95% confidence interval for the treatment difference based on the FAS not only lies above the non-inferiority limit (-10.0%) but also above zero then there is evidence of superiority in terms of statistical significance at the 5% level. In this case, the p-value from the test for superiority will be reported and it will be claimed that FE 999049 is superior to GONAL-F for the primary endpoint analysed. The result based on the PP analysis set is not essential for the superiority claim but should lead to a comparable result for a robust interpretation.

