#### 3.2 Determination of Sample Size

The primary objective of this trial is to demonstrate non-inferiority of FE 999049 compared with GONAL-F with respect to ongoing pregnancy rate in women undergoing controlled ovarian stimulation. The non-inferiority limit for the difference between treatments (FE 999049 versus GONAL-F) is -10.0% (absolute) for the primary endpoint.

Since this is a non-inferiority trial, the full analysis set (FAS) and the per-protocol (PP) analyses are equally important, i.e. non-inferiority should be established for both analysis sets in order to have a robust conclusion. Therefore, the expected proportion of subjects with major protocol deviations should be taken into account when setting the total sample size for the trial. The proportion of subjects with major protocol deviations is assumed to be at most 8%.

The trial is designed to have 90% power of achieving the primary objective for the overall Pan-Asian trial population and 80% power in the Chinese population. The number of subjects needed to achieve 90% power depends on the assumptions regarding the ongoing pregnancy rate. Based on an assumed ongoing pregnancy rate of 32.2% observed in the PP population of the ESTHER 1 trial, N=918 subjects are required in the PP population to obtain a power of 90%. Anticipating at most 8% major protocol deviations this results in N=1000 subjects to be randomised. The power is reasonably robust against deviations from the ongoing pregnancy rate assumption of 32.2%: a 35% ongoing pregnancy rate would still result in a 88.9% power, while lower rates will only increase the power (e.g. 30% yields 91.1% power). Recruiting at least 740

subjects in China is expected to secure that consistency can be established between the results from the overall Pan-Asian trial population and the Chinese trial population. In addition, to obtain approval in other Asian countries at least 260 subjects are needed. Thus a total sample size of 1,000 subjects will be recruited for this trial.

A blinded sample size reassessment will take place when data on the primary endpoint are available for 70% of the planned subjects or when 800 subjects are randomised, whichever comes first. The sample size reassessment will be done without breaking the blind and without inflating the type I error of the trial, in line with the current regulatory guidelines for non-inferiority trials by FDA and in general by EMA.

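### The 90% power given for meeting the primary objective is that of the PP test alone; with FAS and PP both required it is about 89% at the 8% exclusion ceiling

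*Protocol*

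**What the plan says.** **The power statement.** Protocol 9.1 opens its power claim with "The trial is designed to have 90% power of achieving the primary objective for the overall trial population and 80% power in the mainland" (the sentence ends by naming the mainland subjects as a population). SAP 3.2 repeats it as "90% power of achieving the primary objective for the overall Pan-Asian trial population and 80% power in the Chinese population". The synopsis (Statistical Methods) ties the 90% to the primary objective overall. It then gives 80% for mainland China without saying again what that is the power for.

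**The success rule.** Protocol 9.7.2 rejects the null hypothesis if the lower confidence limit "is greater than the non-inferiority limit (-10.0%) for both the FAS and the PP analysis set". SAP 9.2.1 has the same rule. Under Considerations for Sample Size, the protocol treats the two sets as of equal weight and says "non-inferiority should be established for both analysis sets in order to have a robust conclusion".

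**The calculation.** Table 9-2 is a table for the PP set, and the text below it says "N=918 subjects are required in the PP population to obtain a power of 90"%. That number is then raised to 1,000 to allow for major deviations in at most 8% of subjects. Neither document gives the probability that the FAS and PP tests both succeed.

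**Mainland China.** The figure of 740 is a minimum and has no calculation behind it. Protocol 9.7.1 and SAP 9.1 treat the mainland result as supportive.

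**The concern.** A power for achieving an objective should be the probability that the rule defining success is satisfied. Here the rule has two parts, and the quoted power belongs to one of them. The PP set is contained in the FAS, so the two estimates are highly correlated but not identical. The chance that both pass is therefore lower than the chance that PP passes, unless the FAS test passes every time PP does. Raising the number randomised so that PP alone reaches 90% does not cover the second condition.

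What is at stake is the accuracy of a stated design property. Type I error, the analysis and the validity of any claim are not affected.

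**Working it through.** **Inputs**
- Margin: "The non-inferiority limit for the difference between treatments (FE 999049 versus GONAL-F) is -10.0% (absolute) for the primary endpoint" (protocol 9.1).
- Test: "constructing a two-sided 95% confidence interval for the difference in ongoing pregnancy rates" (protocol 9.7.2), so 1.96 is the critical value.
- Rate: "Assuming that the ongoing pregnancy rate is 32.2% in both treatment groups" (protocol 9.1), so the true difference is zero.
- Allocation 1:1 (protocol 4.2.2).
- Randomised: 1,000 overall and 740 in mainland China, each taken as the FAS size.
- Exclusions from PP: 8%, which the plan gives as an upper bound.
- Assumption added here: excluded subjects are a random 8% with the same 32.2% rate, and there is no age effect.

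**1. Reproduce the plan.** Per-arm n = (1.96 + z)² × 2 × 0.322 × 0.678 / 0.10².
- 90% power (z = 1.2816): 10.507 × 0.43663 / 0.01 = 458.8, so 459 per arm and 918 in total.
- 80% power (z = 0.8416): 7.849 × 0.43663 / 0.01 = 342.7, so 343 per arm and 686 in total.

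Both agree with Table 9-2, and all 14 of its per-group cells reproduce in the same way. Then 918 / 0.92 = 998, or about 1,000.

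**2. Power of each test alone.** Power = Φ(0.10 / √(2 × 0.322 × 0.678 / n) − 1.96), with n per arm.
- Overall FAS, n = 500: Φ(3.384 − 1.960) = 92.3%.
- Overall PP, n = 459: Φ(3.242 − 1.960) = 90.0%.
- Mainland FAS, n = 370: Φ(2.911 − 1.960) = 82.9%.
- Mainland PP: 740 × 0.92 = 681 in total, n = 340.5: Φ(2.793 − 1.960) = 79.7%. The 681 is below the 686 that Table 9-2 requires for 80%.

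**3. Both tests together.** Because PP is nested in FAS, the correlation of the two estimates is √(n_PP / n_FAS). Overall this is √(918/1000) = 0.958; in mainland China it is √(681/740) = 0.959. The bivariate normal probability that both pass is:
- Overall: 89.1% with 918 in PP, 89.2% with 920.
- Mainland China: 78.0%.

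A simulation of 2,000,000 trials with the unpooled interval and no age strata gives 89.1% and 78.0%.

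**4. Sensitivity of the joint power.** In the last three rows the PP rate stays at 32.2%.

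| Exclusions from PP | Overall, 1,000 | Mainland, 740 |
|---|---|---|
| 8%, same rate | 89.1–89.2% | 78.0% |
| 6%, same rate | 89.8% | 79.0% |
| 4%, same rate | 90.5% | 80.0% |
| 0% | 92.3% | 82.9% |
| 8%, excluded never conceive | 90.1% | 79.7% |
| 8%, excluded conceive at 20% | 89.5% | 78.7% |
| 8%, excluded conceive at 50% | 88.8% | 77.5% |

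When excluded women never conceive, FAS passed whenever PP passed in the simulation, so the joint power equals the PP power.

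**The case against.** The strongest reply is that the gap is within the precision of a planning figure and that the documents already show which set drives the number. Table 9-2 is labelled for PP, and the 918 is described as a PP requirement. Sizing on the smaller of two nested sets is a common and visible approximation. This stands as an argument on importance. It does not remove the mismatch, because the sentence that states the power ties it to the objective, and the objective needs both sets.

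Three further limits also stand.

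- **The 89% is not the plan's single prediction.** Eight per cent is a ceiling: joint power reaches 90.0% overall at 5.5% exclusions. Random exclusion at an unchanged rate is an added assumption. So is the absence of an age effect, although the primary analysis is stratified by age. An assumed gradient of 37/28/17% across the age strata would bring joint power to 90.1% overall and 79.2% in mainland China. The documents give no rates by age, so that is only an illustration.
- **A reader might infer that mainland China fails a formal 80% target.** The documents do not support this. Protocol 9.7.2 evaluates non-inferiority in the overall population, and the mainland result has no pass or fail rule. Requiring both sets there is one reading of protocol 9.1, and the synopsis wording does not compel it. Moreover, about 0.3 points of the 2-point gap arise because 681 is below 686, which has nothing to do with joint testing. Since 740 is a minimum, more may be recruited.
- **A reader might infer that the blinded sample size reassessment needs the same correction.** Protocol 9.10 and SAP 3.2 recalculate the number of subjects from the observed rate and do not plan to report a power, so there is no power statement there to amend.

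**Conclusion.** The point holds as a labelling error with a small numerical consequence. The 90% is the PP-set power. The power to meet the objective as defined is about 89% overall, roughly one point lower, given 32.2% in both arms, 1,000 randomised and the full 8% excluded at random. With fewer exclusions, or if excluded women rarely conceive, it is at or slightly above 90%.

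For mainland China, 740 randomised with 8% excluded gives about 79.7% in the PP set, and about 78% if both sets had to pass. No formal claim depends on either figure.

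A reader might go further and conclude that the trial is underpowered or that the sample-size tables are wrong. Neither follows. The tables reproduce exactly, and 90% joint power at the 8% ceiling would take only about 1,030 randomised (778 for 80% in mainland China).

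**What to change.** Keep the sample size. In the synopsis, protocol 9.1 and SAP 3.2:

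- Describe 90% and 80% as powers of the PP-set test.
- Add that the power for FAS and PP both to exclude -10.0% is about 89% overall, at 32.2% in both arms with 1,000 randomised and 8% excluded at random. Note that 8% is an upper bound and that 4% exclusions give about 90.5%.
- For mainland China, state that 740 randomised gives about 79.7% PP-set power, and about 78% if both sets are required. Say that this evaluation is supportive.

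The reassessment text needs no change. The cost is a few sentences and slightly less favourable stated figures; no analysis, sample size or trial procedure changes.

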### Considerations for Choice of Non-inferiority Margin

Assuming that the ongoing pregnancy rate is 32.2% in both treatment groups, then the total number of subjects needed to achieve 90% power is governed by the choice of non-inferiority margin. In order to establish non-inferiority, the two-sided 95% confidence interval must lie entirely above the chosen non-inferiority margin. Therefore, the power of the test is directly related to the width of the two-sided 95% confidence interval. The width of this confidence interval is inversely related to the square root of the sample size, i.e. a quadrupling of the sample size will lead to a halving of the width of the confidence interval. In fact, increasing the sample size with 500 subjects from 100 to 600 reduces the width of the confidence band with 59%, while the impact of a similar increase in number of subjects from 1,000 to 1,500 only reduces the width of the confidence band with 18%.

The sample sizes for three different non-inferiority margins are shown in Table 9-1. As shown, changing the non-inferiority margin from -12.0% to -10.0% requires 280 additional subjects, while tightening the margin with an additional 2.0% requires 516 additional subjects. To further illustrate the difference between these three non-inferiority margins, the width of the two-sided 95% confidence intervals and the precision quantified as  $\pm 1$  standard error are also included in Table 9-1. As can be seen, increasing the sample size from 918 to 1,434 subjects reduces the standard error with 0.6 percentage points (from 3.1% to 2.5%).

The relation between the choice of non-inferiority margin and the maximum allowed difference in ongoing pregnancy rates leading to non-inferiority can also be derived. Assuming the observed rate for the GONAL-F group is 32.2% the minimum observed rate in the FE 999049 group that still leads to non-inferiority is shown in Table 9-1. For example, if the non-inferiority margin is -10.0% and the observed ongoing pregnancy rate in the GONAL-F group is 32.2%, then non-inferiority will only be established if the observed ongoing pregnancy rate in the FE 999049 group is at least 28.2%, i.e. the observed ongoing pregnancy rates must not differ with more than 4.0 percentage points. Tightening the margin to -8.0%, (i.e. adding 516 subjects) will require a minimum ongoing pregnancy rate of 29.0% in the FE 999049 in order to claim non-inferiority, i.e. a maximum difference of 3.2 percentage points. Hence, increasing the sample size from 918 to 1,436 subjects reduces the maximum allowable observed difference between treatments by 0.8 percentage points (from 4.0% to 3.2%).

Taking the above into account a non-inferiority margin of -10.0% (absolute) seems appropriate since further tightening of the non-inferiority margin will lead to an increase in sample size with only limited impact on the precision of the estimate and the maximum difference in observed rates leading to non-inferiority.

